For those randomized to the control arm, colonoscopy will be performed with a conventional colonoscope. During withdrawal in the control group, the colon will be inspected using the forward-facing view (standard of care). The colonoscope will then be re-advanced to the cecum and again withdrawn using the forward-facing view.

Patients will be randomized equally to either the new colonoscope (Pentax Retroview) or the control arm with a standard pediatric colonoscope. A total of 300 subjects will be enrolled.

V. STUDY PROCEDURES

1. Patients with prior history of colon polyps (adenomas) are referred for surveillance colonoscopy (standard of care) due to personal history of colon polyps found during colonoscopy done 3 or more years previously
2. The patients will undergo standard bowel preparation for colonoscopy (standard of care)
3. Patients will be asked during routine pre-procedure examination for colonoscopy if they are interested in participating in the study
3. Following consent, patients will be randomized to colonoscopy with either the new colonoscope or conventional colonoscope.
4. Patients will undergo colonoscopy (standard of care). All colonoscopies will be performed by a GI attending.

For those randomized to the new colonoscope, the colonoscope will provide a forward-facing view of the colon during advancement to the cecum (standard of care). The scope will then be withdrawn all the way to the rectum and the colon will be inspected using the forward-facing view (standard of care). The colonoscope will then be re advanced to the cecum and be withdrawn using the retrograde view. In subjects that are randomized to the Retroview scope, the scope is advanced to cecum and then withdrawn to rectum in forward position. The subject is reintubated. At the cecum, scope is retroflexed and withdrawn till before hepatic flexure. Then straightened out, pulled through flexure and retroflexed again. The scope is withdrawn through transverse in retroflexed view until the rectum. There has been a 50 subject trial in which the withdrawal time was recorded and an additional 9.8 minutes were added to the total withdrawal time. It is unknown if there is additional risk in the retroflexed view.

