For those randomized to the control arm, colonoscopy will be performed with a conventional colonoscope. During withdrawal in the control group, the colon will be inspected using the forward-facing view (standard of care). The colonoscope will then be re-advanced to the cecum and again withdrawn using the forward-facing view.

During colonoscopy, any polyps that are found will be removed and any cancers noted will be biopsied (standard of care). 300 patients will be recruited at each site (Stanford and MGH), and the number of precancerous lesions (polyps) and cancers found at colonoscopy utilizing the two different colonoscopes will be evaluated. The adenoma detection rate (ADR), the adenoma per colonoscopy (APC) rate and the adenoma miss rate (AMR) at first pass for the two colonoscopes will be calculated.

The major endpoints are number of precancerous or cancerous lesions found during colonoscopy. We do not plan to terminate the study before enrollment has been met. The study will be terminated at the enrollment of 300 participants at each of the two sites.

6. Data sources will include procedure report, patient's electronic medical record, pathology reports and demographic information. These will be recorded in a confidential manner with PHI de-identified.

Inclusion Criteria:

1. Ability to provide informed consent
2. Adult men and women age 40 years old or older
3. Colonoscopy patients with a history of adenomatous colorectal polyps and are returning for a follow up colonoscopy 3 yrs or more after their previous procedure

Exclusion Criteria:

1. Poor or fair bowel preparation
2. Difficult first insertion of colonoscope
3. Conserved status
4. Familial polyposis
5. Inflammatory bowel disease
6. Pregnancy
7. Active GI bleeding
8. Prior colonic or rectal resection (colon not intact)
9. Screening colonoscopy
10. Colonoscopy done to evaluate symptoms like abdominal pain, diarrhea, constipation, change in bowel habit.

VI. BIostatistical Analysis

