The primary endpoint is the adenoma detection rate (ADR) for the control and Retroview group. The ADR is the percentage of patients with at least one adenoma. The numbers will be compared using standard statistical analysis of proportions (e.g., <http://www.ltconline.net/greenl/courses/201/estimation/ciprop.htm>). Both groups will be assumed to be normally distributed. Secondary endpoints will be the ADR for each pass of the colonoscope (i.e., the incremental adenoma pick-up rate), the overall polyp detection rate (adenomas and non-adenomas) and the mean number of adenomas identified per patient with polyps. We hypothesize that the Retroview colonoscope will detect additional adenomas at a rate of 30% compared to the a rate of 20% when using a

conventional colonoscope. Assuming a significance level of 5% and a power level of 80%, 294 patients in each arm (total of 588 patients) would be required to demonstrate this improved performance.

VII. RISKS AND DISCOMFORTS

The risk of perforation of the colon during screening/surveillance colonoscopy with polypectomy is 1:1000. There is risk of bleeding following polypectomy, but bleeding is readily fixable. These risks would apply to the patients regardless of whether they choose to participate in the study or not. It is not anticipated that participation in this study will directly pose any psychological risks to the patient.

VIII. POTENTIAL BENEFITS

The potential benefits to study subjects will be an improved colonoscopy with fewer missed precancerous (polyps) and cancerous lesions. In addition, both arms of the study will benefit by a more thorough examination of the colon (second look colonoscopy), as data from numerous studies confirms that a second look increases the number of precancerous polyps that are detected at colonoscopy. Identification of an improved colonoscope may aid future patients who undergo screening and surveillance colonoscopy in order to prevent colorectal cancer.

IX. MONITORING AND QUALITY ASSURANCE

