This study will be closely monitored by [name], Director of Quality Assurance for the MGH GI Unit and [name], the Principal Investigator of this study. [name] oversees Quality Assurance for all gastrointestinal endoscopic procedures and [name] as the Principal Investigator of this trial, will be responsible for ensuring that the study is conducted according to the IRB-approved protocol and regulations, and for protecting the rights, safety and welfare of the subjects. [name] or another physician investigator will be responsible for obtaining informed consent from study participants. [name] will be responsible for reporting any adverse events to the IRB. In accordance with Partners Human Research Committee (PHRC) guidelines, adverse events will be reported to the PHRC along with appropriate forms within the required time frame. [name] is the principal investigator of this study and is directly responsible for the conduct of the study.

This is a two site study. When 100 subjects have been enrolled at a site, de-identified study data will be jointly reviewed by the lead investigators at the two sites. Any serious adverse event will be reviewed by the two lead investigators within 48 hours. The two lead investigators will be responsible for determining whether the research should be altered or stopped.

X. REFERENCES

Embedded within the body of this document.

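### Does the review at 100 subjects per site, by investigators who may stop the trial, undermine the final 5% test?

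*Combined protocol and SAP*

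**What the plan says.** Section IX describes oversight by the unit's quality assurance director and the principal investigator, adherence to the approved protocol, subject welfare, and reporting of adverse events to the ethics board. It then adds three provisions in sequence:

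- Scheduled review, tied to enrolment: "When 100 subjects have been enrolled at a site, de-identified study data will be jointly reviewed by the lead investigators at the two sites".
- Harms, as a separate provision with its own time limit: "Any serious adverse event will be reviewed by the two lead investigators within 48 hours".
- Authority to act, placed directly after the provision on harms: "The two lead investigators will be responsible for determining whether the research should be altered or stopped".

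Section V bears on how these are read. On early stopping it says "We do not plan to terminate the study before enrollment has been met", and it ends the study at 300 participants per site. On confidentiality of the data sources it says "These will be recorded in a confidential manner with PHI de-identified". On the retroflexed withdrawal it says "It is unknown if there is additional risk in the retroflexed view".

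Section VI gives one comparison of proportions for the primary endpoint, ADR, and a fixed sample size: "Assuming a significance level of 5% and a power level of 80%, 294 patients in each arm". It mentions no interim analysis, boundary or adjustment of the 5% level.

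**The concern.** Three features together resemble an unplanned interim efficacy analysis. The review is of study data in general, and the data sources in Section V include procedure and pathology reports, which hold the primary endpoint. The removal of identifiers concerns patient identity, so it does not hide the arm, and no masking is described. The people who see the data also hold the power to change or stop the trial, with no stated criterion.

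If the two lead investigators saw ADR by arm and acted on it, the final test would lose its stated error rate. A reader could not then tell whether a change rested on harm or on an emerging difference in detection. Knowledge of interim results could also affect how hard endoscopists search. They already know the arm, because it is the instrument they are using, and the documents give no basis for sizing any extra effect.

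**Working it through.** **1. The plan's own figure.** Inputs from Section VI: rates of 20% and 30%, significance level 5%, power 80%. Sidedness is not stated, so two-sided is assumed. With pooled rate 0.25:

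n = [1.960 × √(2 × 0.25 × 0.75) + 0.842 × √(0.2 × 0.8 + 0.3 × 0.7)]² / 0.10²

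= [1.960 × 0.6124 + 0.842 × 0.6083]² / 0.01 = (1.7122)² / 0.01 = 293.2, rounded up to 294 per arm.

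This matches the plan. A one-sided test would give 231. The sample size is therefore a fixed-sample figure with no allowance for interim testing, which agrees with Section VI describing only one comparison.

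**2. What an unadjusted efficacy look would cost.** This is hypothetical, because no such look is planned. Let t be the fraction of the final sample seen at the look. Under the null, the interim and final statistics have correlation √t, and for one look:

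overall type I error = 1 − P(|Z₁| ≤ 1.96 and |Z₂| ≤ 1.96).

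The trigger is set per site, so the timing is an assumption: 100 subjects overall, 200 overall (both sites pooled), or both. The final total is 600 under Section V. Section IV instead says "A total of 300 subjects will be enrolled", so both totals are shown.

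| Looks tested at 5% | Final total 600 | Final total 300 |
|---|---|---|
| One, at 100 | 9.3% | 8.8% |
| One, at 200 | 8.8% | 7.7% |
| Two, at 100 and 200 | 11.9% | 10.7% |
| None (review not used for efficacy) | 5% | 5% |

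**3. What the text provides for.** The first three rows of the table need ADR to be tabulated by arm, tested at 5%, and acted on. The provisions compare with those steps as follows:

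- *Tabulation by arm.* No section mentions it at the review. It is not forbidden either.
- *Testing.* Section VI has one comparison and no interim test.
- *Action on the result.* Section V says early termination is not planned. In Section IX the authority to change or halt directly follows the sentence on serious adverse events, in a section about monitoring and quality assurance. Its natural reading is authority to act on harm.

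The last row of the table is therefore the one that describes the plan.

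**4. Would an efficacy look at that point be tempting?** At the plan's rates, the 95% half-width for the difference in ADR is:

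- 100 per arm: 1.96 × √(0.16/100 + 0.21/100) = 0.119, or 11.9 points.
- 50 per arm (one site at its trigger): 1.96 × √(0.16/50 + 0.21/50) = 0.169, or 16.9 points.

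Both exceed the 10-point difference the trial is designed to detect, so such a look would tell the investigators little about efficacy.

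**The case for a change.** The best argument for acting is that the omission is certain even though the harm is conditional. Safety already has its own routes in Section IX: review of each serious event within 48 hours, reporting to the ethics board, and quality assurance oversight. The review at 100 subjects is additional and is not confined to adverse events. Section V's sentence on termination states an intention. It does not cover alterations short of stopping, or limit what is viewed. Even if safety is the purpose, harms by arm are not named, although the risk of the retroflexed view is said to be unknown. Two or three sentences would close the gap at almost no cost.

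Part of this stands: the purpose, content and masking of the review are unwritten, and Sections V and IX would read better together if they were stated. The inference to an efficacy look does not stand. Prompt review of single events and periodic review of accumulated data are complementary, so providing for the first does not make the second an efficacy analysis. Authority to stop for harm is also compatible with having no plan to stop early.

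A rule confining the review to harms would have a cost of its own. It would exclude protocol adherence, data completeness and enrolment, which are ordinary business under that section's title. At the perforation risk of 1 in 1,000 in Section VII, 100 to 200 subjects give only 0.1 to 0.2 expected perforations, so that part of a harms table would be nearly empty. A formal efficacy boundary would serve an analysis that nobody has proposed.

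**Conclusion.** The concern does not call for a change. Section IX leaves the scope of a monitoring review unwritten, and the investigators can fill that gap sensibly by reviewing safety and study conduct. The primary analysis remains one comparison at 5% on a sample size that reproduces exactly.

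The inflation to between 7.7% and 11.9% measures a rule the documents do not contain. It should not be cited as a defect of this trial. The conclusion rests on reading the review in its monitoring context, and on ADR by arm not being compared and acted on before enrolment is complete. If that did happen, the 5% level could no longer be relied on and the report would need to say so. Stating the scope in Section IX would be an optional courtesy to readers, since no analysis in the plan depends on it.
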